5.1.1.3 Treatment assignment and treatment groups

Treatment assignment for the SS and PK-PPS will be based on the actual treatment received in each Dosing Period.

Listings will be presented by treatment sequence, unless otherwise specified.

Summaries will be presented by treatment sequence or treatment group and overall, where applicable. The following order will be used in the Tables, Figures and Listings (TFLs): tablet, dry syrup and overall, where applicable.

For analysis conducted using the ES, an additional group for participants not randomized may be displayed, as applicable.

5.1.1.4 Center pooling strategy

Not applicable since this study will be conducted at a single site.

5.1.1.5 Coding dictionaries

All AEs and medical history will be coded for analysis according to the Medical Dictionary for Regulatory Activities (MedDRA®) coding dictionary, using the MedDRA version 18.1. Prior and concomitant medications will be coded for analysis using the World Health Organization Drug Dictionary (WHO-DD) version Sep. 2017. Medical procedures will not be coded.

5.1.1.6 Multicenter studies

Not applicable since this study will be conducted at a single site.

5.1.1.7 Handling of dropouts or missing data

Missing data will not be imputed unless otherwise stated. Data from subjects who prematurely discontinue the study will be used to the maximum possible extent.

Partial dates for concomitant medication and AEs will be imputed as described in Section 6.3 and Section 10.2.

5.2 Participant Dispositions

Participant screening and primary reason for screen failure will be summarized using the ES. The summary will include the following:

- Number of participants screened
- Number and proportion of participants with screen failures
- Number and proportion of screen failures by primary reason for screen failure

Disposition of participants screened will be summarized using the ES. The number and percentage of participants in each analysis set by treatment (tablet or dry syrup) will be calculated based on the RS.

Participants who have started the study, completed the study and discontinued the study will be summarized using the RS by treatment sequence. The summary will include the following:

- Number of and proportion of participants who have started the study
- Number of and proportion of participants who have discontinued the study
- Number of and proportion of participants who have completed the study.
- Number of and proportion of participants who have discontinued the study by primary reason.

Participants that started the study are defined as participants that were randomized and dosed.

Participants completing the study are those participants completing all Treatment Periods of the study as well as the SFU assessment.

By-participant listings of participant disposition will be provided by treatment sequence for ES, and will include the following:

- Study termination/completion status
- Date of informed consent
- Date of randomization
- Date and time of IMP administration
- Date of premature study termination for successfully screened participants dropping out of the study
- Date of screen failure for screen failure participants
- Treatment (Period) at discontinuation
- Primary reason for premature study termination, as applicable
- Primary reason for screen failure, as applicable.

By-participant listings of visit dates will be presented by treatment sequence using the RS.

By-participant listings of participant who did not meet study eligibility criteria will be presented overall using the ES.

By-participant listings of participant inclusion in each analysis set will be presented overall using the ES. By-participant listings of participant excluded from each analysis set will be presented by treatment sequence including the reasons for exclusion; the listing will be based on all subjects in the RS.

6 DEMOGRAPHICS AND OTHER BASELINE CHARACTERISTICS

6.1 Demographics and other baseline characteristics

Demographic variables including age, gender, race (Asian), ethnicity (not Hispanic or Latino), height (cm), body weight (kg), and body mass index (BMI: kg/m²) will be listed by treatment sequence for all participants in the ES. Age will be used as recorded on the electronic case report form (eCRF) and will not be recalculated.

Demographic and the other baseline characteristic variables at Screening will be summarized by treatment (tablet or dry syrup) and overall based on the SS.

The continuous variables will be summarized using descriptive statistics, and the categorical variables will be summarized using frequency counts and percentages.

Age will be summarized in both continuous and categorized (as per clinicaltrials.gov requirements) format.

For the clinicaltrials.gov reporting, the age categories will include:

- ≤ 18 years
- 19 to < 65 years
- ≥ 65 years

By-participant listings of lifestyle data will be provided for the RS.

Viral serology will be listed based on the ES.

6.2 Medical history and concomitant diseases

By-participant listings of previous and ongoing medical history and procedure history will be provided for the RS. Medical history will include MedDRA SOC and PT, reported condition, start date and stop date (or status ongoing, as applicable). Hepatic event supplemental medical history will be listed.

6.3 Prior and concomitant medications

Prior and concomitant medications will be listed by treatment sequence and participant for participants in the RS and will include the reported term, the anatomical therapeutic chemical (ATC) subgroup (level 1 and 3), preferred term, dose and dose unit, frequency, formulation, indication, prior or concomitant classification flag, start and stop dates (including relative day calculated as described in Section 5.1.1.1.1), duration (unit: day, calculated as stop date – start date + 1) and treatments assigned to. A glossary of medication terms including reported term, preferred term, and ATC levels 1 and 3 will also be presented. Data handling will be described in Section 11.1.4.

Prior and concomitant medications will be summarized separately for the SS by treatment (concomitant medications only) and overall, ATC code (level 1 and 3), and preferred term, including the number and percentage of subjects receiving each medication as categorized by the ATC subgroup or preferred term. The denominator for percentages will be the number of subjects in the SS for each treatment group.

In the case of missing dates, the classification of medications as prior or concomitant will be performed after imputation of dates as described below. Imputations of missing dates will be performed prior to calculation of relative days.

The following rules are applied to impute partial start dates for medications:

- If only the month and year are specified and the month and year of first IMP dose is not the same as the month and year of the start date, then use the 1st of the month.
- If only the month and year are specified and the month and year of first IMP dose is the same as the month and year of the start date, then use the date/time of first IMP dose.
- If only the year is specified, and the year of first IMP dose is not the same as the year of the start date, then use January 1 of the year of the start date.
- If only the year is specified, and the year of first IMP dose is the same as the year of the start date, then use the date/time of first IMP dose.
- If the start date is completely unknown, then use the date/time of first IMP dose.

The following rules will be applied for partial stop dates and will be imputed for the calculation of duration of each medication:

- If only the month and year are specified, then use the last day of the month.
- If only the year is specified, then use December 31 of that year.

- If the stop date is completely unknown, do not impute the stop date. In this case the medication will be assigned to all Dosing Periods subsequent to the medication start date.

Concomitant medications will be assigned to Dosing Periods, based on the time when the medication is taken. Assignment to Dosing Periods will be done after missing dates have been imputed as described above. Concomitant medications will be assigned to a treatment based on the treatment received in the Dosing Periods as follows:

- Dosing Period 1: the start or end date is on or after IMP administration in Dosing Period 1 and prior to IMP administration in Dosing Period 2
- Dosing Period 2: the start or end date is on or after IMP administration in Dosing Period 2.

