6.5 Concomitant medication(s)/treatment(s)

6.5.1 Permitted concomitant treatments (medications and therapies)

Paracetamol (acetaminophen) for the treatment of mild symptoms (eg, headache or pain relief) not exceeding 1g per dose is permitted with a total of 10g within 2 weeks and until 48 hours before the first administration of IMP.

Study participants will be allowed to receive a COVID-19 vaccine up to 7 days prior to the initiation of IMP administration. Vaccine administration will be entered as a prior medication in the eCRF. Study participant continuation in case of a vaccine-related AE will be as per Investigator judgement.

Except for the medications noted above, no concomitant medication is allowed during this study.

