10.2 Adverse Events

All AEs will be coded using the Medical Dictionary for Regulatory Activities (MedDRA®) and characterized as pretreatment and treatment emergent according to the intake of the IMP.

Adverse events with a start date prior to the first dose of IMP will be defined as pre-treatment AEs. A TEAE is defined as any AE with a start date/time on or after the first dose of IMP or any unresolved event already present before administration of IMP that worsens in intensity following exposure to IMP.

Imputed dates will not be shown in the listings; all dates will be displayed as reported in the database.

The following rules will be applied for partial start dates and time:

- If only the month and year are specified and the month and year of the first dose of IMP is not the same as the month and year of the start date, then use the 1st of the month, or the date of Screening if this is later (if the latter imputation results in an end date that is earlier than the start date, then use the 1st of the month). If time is missing this will be imputed as 00:00 h
- If only the month and year are specified and the month and year of the first dose of IMP is the same as the month and year of the start date, then use the date of the first dose of IMP. If this results in an imputed start date that is after the specified end date, then use the 1st of the month, or the date of Screening if this is later (if the latter imputation results in an end date that is earlier than the start date, then use the 1st of the month). If the imputed date is the date of dosing then time will be imputed as the start time of the dosing (i.e., event will be regarded as treatment-emergent)
- If only the year is specified, and the year of the first dose of IMP is not the same as the year of the start date then January 01 will be used. If time is missing this will be imputed as 00:00 h
- If only the year is specified, and the year of the first dose of IMP is the same as the year of the start date, then the date of the first dose of IMP will be used. If this results in an imputed start date that is after the specified end date, then January 01, or the date of Screening if this is later will be used (if the latter imputation results in an end date that is earlier than the start date, then January 01 will be used). If the imputed date is the date of

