11.1.4 Prior/concomitant/follow-up medications

If a participant takes a medication before the study medication administration, this medication will be categorized as 'prior medication'. This includes medications that started prior to study medication administration and continued after.

Medication not stopped before the date of study medication administration will be classified as 'concomitant medication'. Medication will also be labeled as 'concomitant medication' when the start date is between the date (including the date) of study medication administration and the date of the participant's last study visit.

From the definitions above, any medication that started prior to dosing and continued after dosing will be classified as both prior and concomitant.

Any medications with missing dates and/or times will be handled as described in Section 6.3 in order to classify them as prior or concomitant.

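### SAP 6.3 can impute a medication start later than its recorded stop; any such record gets a false concomitant flag, a Period 1 assignment and a zero or negative duration

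*SAP*

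**What the plan says.** SAP 6.3 gives three situations in which the start of a medication is set to the first IMP dose:

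- month and year recorded, and the month and year of first dose "is the same as the month and year of the start date, then use the date/time of first IMP dose";
- year only recorded, and "the year of first IMP dose is the same as the year of the start date, then use the date/time of first IMP dose";
- nothing recorded: "If the start date is completely unknown, then use the date/time of first IMP dose".

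None of the three depends on the stop date. The same section says that prior/concomitant classification, relative days and assignment to a Dosing Period all come after imputation. Duration is "calculated as stop date – start date + 1". A medicine belongs to Dosing Period 1 if "the start or end date is on or after IMP administration in Dosing Period 1 and prior to IMP administration in Dosing Period 2", so either date is enough.

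SAP 11.1.4 has two routes to the concomitant label. The first is that the medicine had not been stopped before the dosing date. The second applies "when the start date is between the date (including the date) of study medication administration" and the last study visit. For missing dates it refers back to 6.3.

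The adverse event rules in SAP 10.2 use the same default but add a check against the end date: "If this results in an imputed start date that is after the specified end date, then use the 1st of the month", or the Screening date if that is later. Parallel checks cover the year-only and unknown-start cases.

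**The concern.** Imputing to the first dose is a reasonable cautious default when nothing shows that the medicine ended earlier. It is not reasonable when a recorded stop shows that it did. The SAP handles this for adverse events but not for medications, although SAP 5.1.1.7 names the two sections together as its rules for partial dates.

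Medicines that end before dosing are expected in this trial. Protocol 6.5.1 says that paracetamol "is permitted with a total of 10g within 2 weeks and until 48 hours before the first administration of IMP". Occasional use with an exact last day and only a rough first day is a plausible record.

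At stake is the accuracy of the medication listing (relative day, duration, classification flag, treatment assigned) and of the concomitant medication table by formulation. A medicine finished before either formulation was given could be counted against tablet or dry syrup.

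**Working it through.** The documents state no figure here, so the check applies the rules in the order the SAP sets. Calendar dates are assumed for illustration.

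**General result.** Let dose 1 be on day D and the recorded stop on day D − k, with k of at least 1, and let the start be incomplete in one of the three ways above.

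1. Imputed start (6.3) = D.
2. Duration (6.3) = (D − k) − D + 1 = 1 − k.
3. Concomitant (11.1.4): the first route fails because the medicine stopped before D. The second succeeds because the imputed start is D, so the medicine is flagged concomitant.
4. Dosing Period (6.3): the end date is outside the window but the imputed start is inside it, so the medicine is assigned to Period 1 and to the formulation given then.

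**Simple example.** Dose 1 on 15 June, start recorded as June of that year, stop 10 June: 10 − 15 + 1 = −4 days.

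**Further cases, dose 1 assumed on 20 June 2022**

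| Start recorded | Stop | k | Duration as written | Fallback start | Duration with fallback |
|---|---|---|---|---|---|
| June 2022 | 19 June | 1 | 0 | 1 June | 19 |
| June 2022 | 18 June | 2 | −1 | 1 June | 18 |
| June 2022 | 10 June | 10 | −9 | 1 June | 10 |
| 2022 | 10 March | 102 | −101 | 1 January | 69 |
| Unknown | 10 June | 10 | −9 | needs its own rule | – |

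As written, every row is flagged concomitant and assigned to Period 1. With the fallback, the first four rows have a positive duration, are prior only and carry no Dosing Period.

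**Limits of the trigger.** Paracetamol stopped at the protocol's 48-hour limit has k of at least 2, so an affected paracetamol record gives a negative value. A stop known only to the month of dose 1 is imputed to the end of that month, which is not before dosing, so no negative duration arises.

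**Effect on the table.** The denominator in 6.3 is the Safety Set for each treatment. If all 24 planned participants are in a column, one affected participant adds 1/24 = 4.2 percentage points to that medicine's row.

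**The case against.** The strongest reply is that such records should be rare and easily caught. Both an incomplete start and a known earlier stop are needed. Exclusion criterion 8 and Protocol 6.5.2 bar nearly all medicines for 14 days before dose 1. Medication is recorded at Screening and again at check-in, at one site, and a Data Evaluation Meeting before lock handles data issues case by case. This stands as a limit on frequency, but it does not repair the rule.

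It can also be said that the text does not all point one way. The first route in 11.1.4 would not capture these records, and 6.3 opens its period assignment by referring to when the medicine was taken. That is true, but the second route and the two operative bullets still capture them, and 11.1.4 sends missing dates back to 6.3. The result is a conflict within the SAP, not an override.

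A reader might go further in two ways that the documents do not support:

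- **That prior medication would be undercounted.** SAP 11.1.4 treats anything taken before dosing as prior and allows a record to be both prior and concomitant. A stop before dosing itself shows earlier use. The demonstrable error is an added concomitant flag, not loss of the prior flag.
- **That compliant participants would be recorded as breaching the medication ban.** Neither document derives protocol deviations from imputed dates. Deviations are reviewed on an ongoing basis and at the Data Evaluation Meeting, and the listed stop date would show that the medicine had ended.

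**Conclusion.** The point holds as a minor defect of specification. For a record with an incomplete or unknown start of the kind described and a known stop before dose 1, SAP 6.3 and 11.1.4 as written produce a false concomitant flag, a false assignment to the Period 1 formulation and a duration of 1 − k days. That duration is impossible for k of 2 or more and zero for k = 1.

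This rests on reading the two routes in 11.1.4 as alternatives, which is how they are worded, and on such a record existing. The documents do not allow the number to be estimated; with 24 planned participants and tight medication rules it is probably small, possibly zero.

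The consequence stops at the medication listings and the by-formulation concomitant medication table. Neither the bioequivalence comparison of Cmax and AUC(0-t) nor the TEAE analyses use these dates, so the point should not be read as a threat to the study's conclusions.

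**What to change.** In SAP 6.3, add to the start-date rules that, when the imputed start falls after the recorded stop, the start becomes:

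- the 1st of the month, if month and year are known;
- January 01, if only the year is known;
- if the start is wholly unknown, a stated fallback no later than the stop date. Alternatively, leave the start unimputed and classify on the stop date. The authors need to choose one.

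The 10.2 wording should not simply be pasted in. Its Screening-date clause is not needed, because prior medicines may properly start before Screening.

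In SAP 11.1.4, state that a medication with a known stop before the first IMP dose is prior only and is not assigned to a Dosing Period. This also removes the conflict between the two routes to the concomitant label.

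The cost is a few sentences in the SAP and a small programming change, with no effect on conduct or data collection.

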7 MEASUREMENTS OF TREATMENT COMPLIANCE

Any dosing deviations will be assessed in the Data Evaluation Meeting (DEM) for possible impact on the PK-PPS. No listing will be provided since study participant compliance to treatment will be ensured by the administration of IMP under the Investigator's (or designated site personnel's) supervision.

8 EFFICACY ANALYSES

Not applicable.

9 PHARMACOKINETICS

Pharmacokinetic analyses will be performed on the SS. Statistical analyses will be performed on the PK-PPS.

9.1 Plasma concentration-time profiles

Blood samples will be collected for measurement of plasma concentrations of BRV at predose, and 0.25, 0.5, 0.75, 1.0, 1.25, 1.5, 2, 3, 4, 6, 8, 12, 16, 24, 36, and 48 hours postdose. Allowable deviations from these scheduled PK sampling times are provided in Table 8-2 of the protocol. Individual concentration-time data will be listed for the SS by treatment sequence.

Concentration listings will include nominal PK sampling time, actual sampling times relative to dose administration, deviation from nominal time, and percent deviation from nominal time, and concentrations, day, dosing period and sequence, treatment (tablet or dry syrup).

Percent deviation (%) = (actual time – scheduled time)/scheduled time * 100.

Plasma concentration data will be listed and summarized with the descriptive statistics by treatment (tablet or dry syrup) and scheduled time for the PK-PPS.

Descriptive statistics will include number of study participants (N), number of available observations (n), mean, standard deviation, median, minimum, and maximum, geometric mean, geometric coefficient of variation (CV), and 95% confidence interval (CI) for the geometric mean.

The geoCV will be calculated as $geoCV(\%) = 100 \times \sqrt{\exp\{(lnSD)^2\} - 1}$,

where $\ln SD$ is the standard deviation of the log transformed values.

Graphical displays of individual plasma concentrations by actual time will be presented on semi-logarithmic and linear scales.

Graphical displays of geometric mean concentrations with its corresponding 95% CI (linear scale and semi-logarithmic scale) and zoomed geometric mean concentrations between 0 and 6 hr. will also be presented by treatment (tablet or dry syrup) and scheduled time on semi-logarithmic and linear scales.

Plasma concentrations will be displayed superimposed in a single plot for both treatments. Spaghetti plots will be presented separately for treatment, with profiles for all participants superimposed on the same graph.

Refer to Appendix 2 (Section 11.3.1) for standard reporting procedures of individual values and descriptive statistics for plasma concentration data in listings, tables, and figures.

9.2 Primary/other pharmacokinetic variables

The primary and other PK parameters distinction is given in Section 9.3.1 and Section 9.4.1.

9.2.1 Derivation of primary/other pharmacokinetic variables and descriptive summaries

Pharmacokinetic parameters will be calculated by non-compartmental analysis methods from the concentration-time data using Phoenix® WinNonlin® (Version 8.2) or higher.

Actual sampling times will be used for deriving the PK parameters. Pharmacokinetic parameters will be estimated according to the guidelines presented in Appendix 4, Section 11.4.

According to the definition of the Pharmacokinetic Per-Protocol Set (PK-PPS) (Section 4.4), all randomized study participants who are included in the SS, have no important protocol deviations that are considered to impact the study participant's data validity for analysis of the primary study objective, and have a sufficient number of bioanalytical assessments to calculate reliable estimates for the primary pharmacokinetic parameters for both treatments will be included in the PK-PPS. If study participant's predose concentration is greater than 5% of the corresponding C_{max} value in both Dosing Periods, the study participant will be excluded from the PK-PPS. If this occurs in 1 of the 2 Dosing Periods, but not in the other Dosing Period, data of the other Dosing Period will be used. If vomiting occurs at or before 2 times of the median t_{max} , the study participant will be excluded from the PK-PPS.

The PK parameters will be listed and summarized with descriptive statistics by treatment (tablet or dry syrup) for the PK-PPS. For individual C_{max} , $AUC_{(0-t)}$ and AUC , ratio of test (dry syrup) versus reference (tablet) will be listed by participant and summarized with descriptive statistics for the PK-PPS. Both the primary and other PK parameters will be listed by treatment (tablet or dry syrup) for subjects excluded from PK-PPS, but included in the SS.

The following descriptive statistics will be calculated: mean, SD, geometric mean, geometric coefficient of variation (CV), minimum, median and maximum and 95% confidence interval (CI)

for the geometric mean. The only exception is t_{max} , for which only median, minimum, and maximum will be reported.

Ping pong plots for individual data in the PK parameters (C_{max} , $AUC_{(0-t)}$ and AUC) will also be displayed for the PK-PPS.

Refer to Appendix 3 (Section 11.3.2) for standard reporting procedures of individual values and descriptive statistics for PK parameters in listings and tables.

